10 APPENDIX B - SCENARIOS FOR ASSESSING OVERALL CORRECT FINAL USE OUTCOME

Scenario	Action	Analysis Population	Study Disposition	Assessment for Overall Correct Final Use Outcome*
Participant has “Stop Use and Ask a Doctor” warning and discontinues from study intervention	Participant identifies the “Stop Use and Ask a Doctor” warning on their own or through TASS and completes all assessments associated with Virtual Visit 2	PP	Discontinuation from Study Intervention/ Completed	Correct, Incorrect or Mitigated
Participant has “Stop Use and Ask a Doctor” warning and discontinues from study intervention	Participant identifies the “Stop Use and Ask a Doctor” warning on their own or through TASS and completes sufficient medical and medication history to obtain a final use outcome	PP	Discontinuation from Study Intervention/ Completed	Correct, Incorrect or Mitigated
Participant has “Stop Use and Ask a Doctor” warning and withdraws from study	Participant identifies the “Stop Use and Ask a Doctor” warning on their own or through TASS and does not complete sufficient medical and medication history or all assessments associated with Virtual Visit 2 to obtain a final use outcome	AUS ITT	Withdrawal	Insufficient data to assess Clinician final use outcome is “Missing”
Participant has “Stop Use and Ask a Doctor” warning and asks a doctor	Participant identifies the “Stop Use and Ask a Doctor” warning on their own or through TASS, speaks with a doctor and completes sufficient medical and medication history or all assessments associated with Virtual Visit 2 to obtain a final use outcome	PP	Completed	Correct, Incorrect or Mitigated

Scenario	Action	Analysis Population	Study Disposition	Assessment for Overall Correct Final Use Outcome*
Participant has “Stop Use and Ask a Doctor” warning and asks a doctor and withdraws from study	Participant identifies the “Stop Use and Ask a Doctor” warning on their own or through TASS, speaks with a doctor and does not complete sufficient medical and medication history or all assessments associated with Virtual Visit 2 to obtain a final use outcome	AUS ITT	Withdrawal	Insufficient data to assess Clinician final use outcome is “Missing”
Participant has “Stop Use and Ask a Doctor” warning and does not stop use	Participant does not identify “Stop Use and Ask a Doctor” warning on their own or through TASS and completes all assessments associated with Virtual Visit 2	PP	Completed	Incorrect
Participant has “Stop Use and Ask a Doctor” warning and CMOG identifies and discontinues from study intervention	Participant does not identify “Stop Use and Ask a Doctor” warning but CMOG identifies at 60/120-day call and completes sufficient medical and medication history or all assessments associated with Virtual Visit 2 to obtain a final use outcome	PP	Discontinuation from Study Intervention/ Completed	Incorrect
Participant has “Stop Use and Ask a Doctor” warning which CMOG identifies and withdraws from study	Participant does not identify “Stop Use and Ask a Doctor” warning but CMOG identifies at 60/120-day call and participant does not complete sufficient medical and medication history or all assessments associated with Virtual Visit 2 to obtain a final use outcome	AUS ITT	Withdrawal	Insufficient data to assess??
Participant has “Ask a Doctor” warning and discontinues from study intervention	Participant identifies “Ask a Doctor” warning from DFL or through TASS and completes sufficient medical and medication history or all assessments associated with Virtual Visit 2 to obtain a final use outcome	PP	Discontinuation from Study Intervention/ Completed	Correct, Incorrect or Mitigated

Scenario	Action	Analysis Population	Study Disposition	Assessment for Overall Correct Final Use Outcome*
Participant has “Ask a Doctor” warning and withdraws from study	Participant identifies “Ask a Doctor” warning from DFL or through TASS but does not complete sufficient medical and medication history or all assessments associated with Virtual Visit 2 to obtain a final use outcome	AUS ITT	Withdrawal	Insufficient data to assess Clinician final use outcome is “Missing”
Participant has “Ask a Doctor” warning and does not stop use	Participant does not identify “Ask a Doctor” warning and completes sufficient medical and medication history, or all assessments associated with Virtual Visit 2 to obtain a final use outcome	PP	Completed	Incorrect
Participant has “Do Not Use” warning and discontinues from study intervention	Participant identifies “Do Not Use” warning on their own or through TASS and completes sufficient medical and medication history or all assessments associated with Virtual Visit 2 to obtain a final use outcome	PP	Discontinuation from Study Intervention/ Completed	Correct, Incorrect or Mitigated
Participant has “Do Not Use” warning and withdraws from study	Participant identifies “Do Not Use” warning from DFL or through TASS but does not complete sufficient medical and medication history or all assessments associated with Virtual Visit 2 to obtain a final use outcome	AUS ITT	Withdrawal	Insufficient data to assess Clinician final use outcome is “Missing”
Participant has “Do Not Use” warning and does not stop use	Participant does not identify “Do Not Use” warning and completes sufficient medical and medication history or all assessments associated with Virtual Visit 2 to obtain a final use outcome	PP	Completed	Incorrect

Scenario	Action	Analysis Population	Study Disposition	Assessment for Overall Correct Final Use Outcome*
Participant has an “OK to Use” outcome which CMOG cannot confirm because of the lack of a verified LDL-C retest and participant has been in study <3 months	Because participant has up to 3 months to obtain an LDL-C retest, the CMOG can obtain an “OK to Use” outcome without the need for a verified LDL-C retest value	PP	Completed	Correct, Incorrect or Mitigated
Participant has an “OK to Use” outcome which CMOG cannot confirm because of the lack of a verified LDL-C retest and participant has been in study >3 months	A CMOG final use outcome cannot be obtained due to the lack of a verifiable LDL-C value	AUS ITT	Withdrawal	Insufficient data to assess If CMOG obtains “OK to Use” outcome, the CMOG outcome will be changed to “Missing”. An a priori mitigation for missing LDL-C is possible in this situation
Participant decides to withdraw from study	Participant does not complete sufficient medical and medication history or all assessments associated with Virtual Visit 2 to obtain a final use outcome	AUS ITT	Withdrawal	Insufficient data to assess Participant and Clinician final use outcomes are “Missing.”
Participant is Lost to Follow-Up (LTf)	Participant does not complete sufficient medical and medication history or all assessments associated with Virtual Visit 2 to obtain a final use outcome	AUS ITT	Lost to Follow-Up	Insufficient data to assess Participant and Clinician final use outcomes are “Missing.”

*The mitigation process is the same as the overall mitigation process for the study.

11 APPENDIX C - INITIAL SELF-SELECTION MITIGATIONS

Label Reference	Rationale for Mitigation

Pregnancy alert: Do not use if you are pregnant or breastfeeding. If you become pregnant, stop taking and call your doctor.
 
Participant enters “no” in the Web App but learns at a later date that they were pregnant.
	
Participant did not know they were pregnant at the time they used the Web App. Participants who demonstrate they had knowledge of a pregnancy are not mitigated.

Do not use if you are taking:
 
- any cholesterol lowering and/or triglyceride lowering prescription medicine- cyclosporine (a medicine for your immune system)- warfarin/ COUMADIN® (a blood thinner) 
Ask a Doctor before use if you are taking:
 
- colchicine (a medicine to treat gout)- HIV/AIDS or hepatitis medicines (such as lopinavir, ritonavir or atazanavir) 
Participant enters “no” in the Web App.
	
Participant was not on a medicine at the time they took the TASS assessment but started a medicine subsequently, or the participant was prescribed a medicine but had no intention of taking the medicine.

Do not use if you are taking cyclosporine (a medicine for your immune system).
 
The participant enters “no” into the Web App.
	
In the instance where the participant doesn’t realize that an eyedrop medicine they are using has cyclosporine, they may enter “no” into the Web App. A “no” response will be mitigated to correct because the low concentration and very low systemic absorption of cyclosporine from an eyedrop formulation will not significantly impact rosuvastatin exposure, and therefore not pose a risk to the participant.

Ask a doctor before use if you take:
 
- colchicine (a medicine to treat gout)	
Participant answers ‘yes’ in TASS to taking colchicine but Clinician determines they are not currently taking but had taken within 7 days of completing the TASS.

Label Reference	Rationale for Mitigation

Male 20-75 – Take 1 tablet every day Female 50-75 – Take 1 tablet every day Participant enters an age within 12 months of their correct age.
	
A Participant who enters an age within 12 months of their correct age will be mitigated to a correct response since the benefit risk profile of rosuvastatin will not be impacted.

Web App	Rationale for Mitigation

Are you currently taking a prescription medicine for high blood pressure (also known as “hypertension”)? Participant enters “no” into the Web App.
	
Participant was not on a BP medicine at the time they took the TASS assessment but started a BP medicine subsequently, or the participant was prescribed a BP medicine but had no intention of taking the medicine.

Do you smoke cigarettes? Participant enters “yes” into the Web App.
	
Participant says “yes” in the Web App to smoking cigarettes, but Clinician determines that participant only smokes e-cigarettes.

12 APPENDIX D - USE AND RE-SELECTION MITIGATIONS

Label Reference	Rationale for Mitigation

Pregnancy alert: Do not use if you are pregnant or breastfeeding. If you become pregnant, stop taking and call your doctor.
 
Participant becomes pregnant during the study but does not stop taking the drug and/or does not call doctor.
	
Participant did not know they were pregnant while using the product.

Pregnancy alert: Do not use if you are pregnant or breastfeeding. If you become pregnant, stop taking and call your doctor.
 
Participant enters “no” in the Web App but learns during the final visit that they were pregnant.
	
Participant did not know they were pregnant at the time they used the Web App.

Do not use if you had a heart attack, stroke, peripheral artery disease (PAD) or an operation or procedure on your heart.
 
Participant enters “yes” in the Web App.
	
While the participant believes, based on their history, that they had one of these events, the CMOG physician determines that it was not a true event. The “yes” response will be mitigated to correct because the participant believed they were giving a correct response and their response was a conservative response, which results in them not qualifying for Crestor OTC. In this case, no medical harm can come to the participant based on this response.

Do not use if you are taking:
 
 - any cholesterol lowering and/or triglyceride lowering prescription medicine - cyclosporine (a medicine for your immune system) - warfarin/ COUMADIN® (a blood thinner) 
Ask a Doctor before use if you are taking:
 
 - colchicine (a medicine to treat gout) - HIV/AIDS or hepatitis medicines (such as lopinavir, ritonavir or atazanavir) 
Participant enters “no” in the Web App.
	
Participant was not on a medicine at the time they took the TASS assessment but started a medicine subsequently, or the participant was prescribed a medicine but had no intention of taking the medicine.


Do not use if you are taking cyclosporine (a medicine for your immune system).
 
The participant enters “no” into the Web App.
	
In the instance where the participant doesn’t realize that an eyedrop medicine they are using has cyclosporine, they may enter “no” into the Web App. A “no” response will be mitigated to correct because the low concentration and very low systemic absorption of cyclosporine from an eyedrop formulation will not significantly impact rosuvastatin exposure, and therefore not pose a risk to the participant.

Label Reference	Rationale for Mitigation

Stop Use and Ask a Doctor if you:
 
 - get severe and unexplained muscle pain, tenderness or weakness - get symptoms of liver problems (upper belly pain, dark urine, yellowing of skin or whites of eyes) 	
While the participant believes, based on their history, that they had one of these events, the CMOG physician determines that it was not a true event. The “stop use” will be mitigated to correct because the participant believed they were taking the correct action and it was a conservative action, which results in them not continuing to take Crestor OTC. In this case, no medical harm can come to the participant based on this action.

Other	Rationale for Mitigation

Lost Opportunity
	
Clinician determines it was ok for someone to take the drug but based on responses in the Web App, participant got a “Do Not Use” (DNU) or “Ask a Doctor” (AAD).
 
Participant decides to stop taking study medication and discontinues from the study, but clinician determines that they were “OK to Use”.


Missing LDL-C Retests
 
 - Given consumers can only purchase non-prescription rosuvastatin through the Web App, we can stop shipping medication to individuals who fail to retest after a period of time agreed with FDA. Thus, for participants who qualify for treatment (i.e., have an “OK to Use” outcome or an “Ask a Doctor” outcome and indicates the doctor gave them permission to use the drug) but fail to obtain the necessary verified retest(s) (whether it is an initial retest or a second retest in those with an inadequate response), an a priori mitigation allowing these individuals to be mitigated to a “correct” response is appropriate. This mitigation can only be applied in situations where the CMOG’s outcome was “coded” as “missing” because of a missing LDL-C value, and the CMOG’s TASS outcome would have matched the Participant Outcome if not for the missing LDL-C retest. 	
 1. CMOG final TASS assessment is “OK to Use” or “Ask a Doctor”, but is coded as “Missing” because the participant failed to obtain a verified LDL-C retest or an SMT. 2. CMOG final TASS assessment is “OK to Use” but coded as “Missing” because the participant failed to retest and the SMT was an Inadequate Response, or the participant self-tested with a verified inadequate response result that was used for their Visit 2 reassessment. 3. Participant enters an initial Inadequate Response LDL-C retest into the Web App (verified or unverified), has an “OK to Use” outcome or “Ask a Doctor” outcome, indicates the doctor gave them permission to use the drug and makes a purchase. CMOG final TASS assessment is coded as “Missing” because only one or no verified LDL-C retest value was available for use, but otherwise would have matched the participant outcome. (Table XX, scenarios 1b, 2b, 3a, 3b, 4a, 4b, 7b, 9a, 9b)

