retest for use by the CMOG at Visit 2, an “OK to Use” outcome by the CMOG will be coded as missing since the lack of an LDL-C value means the CMOG can never know for certain that the subject was truly “OK to Use”. The need to recode the CMOG outcome in this instance is a function of the Web App being programmed to allow all subjects to complete the 6 months study regardless of whether they obtained an LDL-C retest. In those situations where the participant has been in the study less than 3 months, a verified LDL-C will not be required for the CMOG to determine an outcome since the DFL allows individuals up to 3 months to obtain an LDL-C retest.

- If the value demonstrates an inadequate LDL-C response (i.e., $\geq 0\%$ and $< 15\%$ reduction), the participant will get an “OK to Use” outcome and be able to order drug, but they will be asked to repeat the LDL-C test. Therefore, individuals with an inadequate response, who proceed to purchase more medication, may have more than one LDL-C value entered into the Web App during the course of the study and the second LDL-C value entered into the Web App could result in one of the following outcomes:
 - If the result is an inadequate response or an increase in LDL-C, the participant will get a “Do Not Use” outcome.
 - If the result is an adequate response, the participant will get an “OK to Use” outcome.
 - If no additional LDL-C value is entered into the Web App, the participant will continue to get an “OK to Use” outcome.

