- For a CMOG final use outcome to be determined as “Ok to Use”, all answers to the questions associated with Do Not Use and Ask a Doctor warnings must be answered as “No”. By default, an “Ok to Use” final use outcome can only be obtained when the CMOG clinician has answers to all the questions that are asked in the TASS tool. This includes having an LDL-C retest with an adequate response for participants who have continued in the study for 3 or more months. Thus, all “OK to Use” final use outcomes should be coming via a TASS assessment.

In those instances where a participant, CMOG or both TASS assessments are missing such that an Overall Final Use Outcome cannot be determined, the impact of the missing information will be assessed using the prespecified sensitivity analyses (see [Section 4.2.2](#)).

Missing CMOG initial TASS assessments should be rare or non-existent. In the event the CMOG is unable to perform a TASS assessment at Visit 1, the CMOG clinician will use the

DFL and follow an algorithm based on the question flow of the TASS tool to make a determination as described above. If the CMOG is unable to make a determination, the initial outcome will be missing.

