 - MC_R = Mitigated Correct Rejector

The denominator for the primary analysis of the second co-primary endpoint will only include those participants in the analysis population with a non-missing final use outcome for the participant and CMOG. The target threshold for this endpoint is that the lower bound of the 95% exact confidence interval needs to be greater than 85% overall.

For the second co-primary endpoint, the PE of the Overall Correct Final Use Outcome, with *a priori* and post-study mitigations, will be reported with a two-sided 95% confidence interval which will be computed using exact binomial (Clopper-Pearson) methods for the proportion of each correct outcome among the entire PP population, with mitigations, overall and by subgroups. The Overall Correct Final Use Outcome will also be evaluated without mitigations and with only *a priori* mitigations on the PP population overall and by subgroups.

An additional exploratory analysis of the Overall Correct Final Use Outcome, with *a priori* and post-study mitigations, will be performed on the PP population for those participants who had both a participant and CMOG final use assessment obtained solely from the Web App. The PE of the Overall Correct Final Use Outcome, with *a priori* and post-study mitigations, will be reported with a two-sided 95% confidence interval which will be computed using exact binomial (Clopper-Pearson) methods for the proportion of each correct outcome among the entire PP population overall and by subgroups. Overall Correct Final Use Outcome obtained

solely from the Web App TASS assessments will also be evaluated without mitigations and with only *a priori* mitigations on the PP population overall and by subgroups.

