The count and percentage of participants and CMOG receiving each TASS outcome at the final use assessment along with the reasons for their outcomes will be presented on the PP population overall and by subgroups. For participants that do not have a TASS outcome at the final use assessment but have provided sufficient verbatim information for discontinuing study intervention prior to study completion that allows for an assessment of the participant final use outcome, the count and percentage of participants receiving each final use outcome at the final use assessment will be presented on the PP population overall and by subgroups. Lastly, for CMOG final use outcomes that were determined by the clinician using the DFL and the available medical and medication history the count and percentage of participants receiving either a “Do Not Use” or “Ask a Doctor” outcome by the CMOG will be presented on the PP population overall and by subgroups.

A separate table will be constructed to display the count and percentages of participants with a least one mitigation (*a priori* and post-study) applied to the second co-primary endpoint. For those participants with at least one mitigation, counts and percentages will be reported for each mitigation descriptor for the PP population overall and by subgroups.

Data listings will be provided for the participant and CMOG TASS entries and TASS outcome at the final use assessment, and overall correct final use assessment.

A sensitivity analysis will be performed for the participants in the AUS ITT population with a missing Overall Correct Final Use Outcome for the second co-primary endpoint (Sensitivity Analysis #1). As the primary analysis for the second co-primary endpoint includes all participants in the PP population, to be included in the primary analysis participants must complete the Virtual Visit 2 or provide sufficient medical history information, and in some instances a verified LDL-C value, to assess a final use outcome for the CMOG. In those cases where a participant has provided insufficient data to allow for a CMOG final use assessment, and thus, results in missing CMOG final use outcome, the Overall Correct Final Use Outcome is not able to be assessed and will be missing. The count and percentage of reasons for a missing participant or CMOG TASS final use outcome from the Web App will be presented for the AUS ITT population overall and by subgroups.

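### Participants with no verified LDL-C after 3 months or more can count as Correct in the second co-primary endpoint, and no listed worst-case or tipping-point run is specified to undo that credit

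*SAP*

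**What the plan says.** **The credit.** SAP Appendix D lists three rationales under Missing LDL-C Retests. The first covers a CMOG result of OK to Use or Ask a Doctor that was coded Missing "because the participant failed to obtain a verified LDL-C retest or an SMT". For the whole group the SAP holds that a "mitigation allowing these individuals to be mitigated to a “correct” response is appropriate", on condition that "the CMOG’s TASS outcome would have matched the Participant Outcome if not for the missing LDL-C retest". Protocol 9.4.1.3, Table 6, carries the same text. Such cases enter the numerator of the second co-primary endpoint as a priori mitigations.

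**What other sections say of the same people.**
- SAP 3.2.3 recodes a CMOG OK to Use to Missing from 3 months on when no verified retest exists, because "the lack of an LDL-C value means the CMOG can never know for certain that the subject was truly" OK to Use. Below 3 months "a verified LDL-C will not be required for the CMOG to determine an outcome", so rationale 1 is not needed there.
- SAP 3.2.3.3, on what the CMOG needs for OK to Use: "This includes having an LDL-C retest with an adequate response for participants who have continued in the study for 3 or more months".
- SAP 4.2.2 on the primary denominator: it "will only include those participants in the analysis population with a non-missing final use outcome for the participant and CMOG".
- SAP Appendix B places a participant with more than 3 months and no verified LDL-C in the AUS ITT set, with disposition Withdrawal and too little data to assess. It then adds that the a priori mitigation is possible.

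**Robustness runs.** SAP 4.2.2: "A sensitivity analysis will be performed for the participants in the AUS ITT population with a missing Overall Correct Final Use Outcome". SAP 4.1.3.2 defines its best-case, worst-case and tipping-point versions. SAP 4.2.2 also plans the endpoint on the PP population without mitigations and with a priori mitigations only, and a table of counts for each mitigation descriptor.

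**The concern.** The same participant is unassessable under one part of the SAP and a success under another. Crediting an unknown outcome as Correct is a best-case imputation inside the primary analysis. By contrast, the first co-primary endpoint counts a missing CMOG outcome as Incorrect.

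The matching condition does not test the part that is unknown. SAP 3.2.3 explains that the CMOG leaves the LDL-C field blank when there is no verified value and that the Web App then returns OK to Use. It also lets a participant who enters no retest keep reordering. On LDL-C, therefore, both sides agree by default, and only some other warning can break the match.

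The endpoint concerns proper use and is tested against an 85% lower bound. If credited cases are not all truly correct, the observed rate is too high. The planned runs may not show by how much, because a mitigated case may no longer count as missing when the imputation is done.

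**Working it through.** **1. The plan's own figure.** Inputs from SAP 1.3: N = 500, null rate 85%, assumed true rate 90%, success if the lower limit of the two-sided 95% Clopper-Pearson interval exceeds 85%. The lower limit for x successes in n is the 2.5% quantile of Beta(x, n − x + 1).
- 440/500 gives 84.82% and 441/500 gives 85.04%, so the pass mark is 441.
- P(Bin(500, 0.85) ≥ 441) = 0.0235, the exact one-sided error rate.
- P(Bin(500, 0.90) ≥ 441) = 0.919, which agrees with the stated power of at least 90%.

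**2. Effect on the false-pass chance.** The documents do not give the number credited under rationale 1. Assume k of 500 are counted Correct whatever the truth, and that the true rate is exactly 85%. A pass then needs at least 441 − k correct among the other 500 − k:

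P(Bin(500 − k, 0.85) ≥ 441 − k)

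| k (assumed) | False-pass chance |
|---|---|
| 0 | 2.3% |
| 10 | 3.5% |
| 25 | 6.3% |

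**3. Effect on one result.** Take 450/500 counted Correct (90.0%, lower bound 87.03%), with m of the 450 credited under rationale 1 (m is assumed).

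| m | Scored Incorrect: (450 − m)/500 | Dropped: (450 − m)/(500 − m) |
|---|---|---|
| 5 | 85.92%, pass | 86.90%, pass |
| 9 | 85.04%, pass | 86.80%, pass |
| 10 | 84.82%, fail | 86.77%, pass |
| 25 | 81.56%, fail | 86.36%, pass |

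Entries are lower bounds. Scored Incorrect, 10 cases (2% of 500) reverse the result. Dropped, the first failure comes at m = 69. Dropping is what the PP run without mitigations does to this group, because their CMOG outcome reverts to Missing and they leave the denominator. That run also removes every other mitigation at the same time.

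**4. Tipping point.** Use the planning numbers as an illustration: 1,000 in AUS ITT, 450 credited Correct, 50 Incorrect, 500 missing. The pass mark is 873/1,000. With all missing cases correct the count is 450 + 500 = 950, so 950 − 873 = 77 missing cases may be incorrect. If m credited cases are scored Incorrect as well, the tolerance is 77 − m: 67 for m = 10 and 52 for m = 25. A tipping-point figure that keeps the credit fixed would report 77 in each case.

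**The case against.** Much can be said for the plan, and four points stand.

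- **The order of mitigation and imputation is not stated.** A reader might infer that no worst-case or tipping-point run can ever reverse the credit. The documents do not support that. The CMOG outcome of these cases stays coded Missing, the worst case in SAP 4.1.3.2 covers all missing data and is explained by a missing CMOG outcome, and Appendix B lists the cases as AUS ITT withdrawals. On that reading the run would reach them. What can be said is that no listed run is specified to do so.
- **The credit is conditional.** A reader might call it a certain success for anyone who skips both tests. It is not: a participant who also misses a Stop Use, Do Not Use or Ask a Doctor warning fails the matching condition. Only the LDL-C component goes untested.
- **The group may be small.** For participants still on OK to Use, or on Ask a Doctor with permission, a study-mandated test is required and Visit 2 is rescheduled without one. A reader might subtract the 450 planned for LDL-C from the 500 planned for final use and take 50 as the number affected, which would give a false-pass chance of 14.5%. Both figures are minima, and they belong to different populations (AUS ITT and PP), so the difference is not an estimate of k.
- **Part of the safeguard is planned.** The PP run without mitigations removes the credit, and counts per descriptor are reported. Failure to retest also lowers the separate retest endpoint, which has a 60% threshold.

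It is also fair that adding these cases to the worst case changes little, since with about 500 of 1,000 missing that run is already near 45%. The mitigation is pre-specified with a stated rationale, part of which is redacted in the protocol. Removing it from the primary analysis is therefore debatable.

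None of this resolves the conflict between the sections, and the planned PP run does not test the cases as Incorrect.

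**Conclusion.** The point holds as an inconsistency with a gap in the sensitivity analyses: SHOULD-FIX. For participants in the study 3 months or more with neither a verified retest nor a study-mandated test, the SAP both denies that a CMOG outcome can be known and allows a Correct in the numerator. The denominator rule, taken literally, leaves them out altogether.

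The size depends on a count that the documents do not give. Under the assumed 10 to 25 of 500, the false-pass chance is 3.5% to 6.3% against 2.3%. This takes the credited cases to have the same 85% true rate as the rest. Because they have already matched on everything except LDL-C, their own rate could be higher, and the excess would then be smaller. From 450/500, 10 cases decide the outcome if scored Incorrect and do not if dropped. The planned runs, as written, show only the second of these.

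The material does not show that the primary analysis is invalid or that the mitigation must be deleted.

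**What to change.** 1. Reconcile SAP 3.2.3, 3.2.3.3, the denominator rule in 4.2.2, Appendix B, and Appendix D with Protocol Table 6, so that each gives one status and one analysis set for these participants. State whether a mitigated case enters the PP denominator.
2. State in SAP 4.1.3.2 that rationale-1 cases are treated as missing in the worst-case and tipping-point analyses of the second co-primary endpoint.
3. Report this endpoint on the PP population in two further forms: with rationale-1 cases scored Incorrect, and with this single mitigation removed while all others stay. Give the number of rationale-1 cases separately from rationales 2 and 3.

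The cost is wording in the SAP and Protocol Table 6 and a small addition to the programmed sensitivity output. No new data are needed. The sensitivity result may be less favourable; the primary analysis can stay as specified.
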